### **8.5.3 Subjects Lost to Follow-Up**

In the case of a subject lost to follow-up, attempts to contact the subject must be made and documented in the subject's files.

Subjects who received at least 1 dose of the study drug, were lost to follow-up, and re-contacted, will be encouraged to rejoin the trial.

- If the subject missed  $\leq$  7 consecutive days of study drug, the subject will be encouraged to continue in the trial as usual.
- If the subject missed  $>7$  consecutive days of treatment, the subject will be encouraged to continue in the trial as usual but will be considered a major deviator.

## 9. PROCEDURES FOR SAFETY AND PHARMACOKINETIC EVALUATIONS

### 9.1 General Considerations

No procedures (including Screening activities) may be performed before informed consent has been obtained, with a copy of the ICF given to the subject and another copy placed in the subject's medical records.

The Investigator will use their judgment when determining the clinical significance of any findings.

### 9.2 Pre-Screening

Sites are encouraged to pre-screen subjects prior to consenting. The FDA guidance regarding which pre-screening procedures may be performed may be found on the FDA web site at: <http://www.fda.gov/RegulatoryInformation/Guidances/ucm126430.htm>.

### 9.3 Screening Period Evaluations

#### 9.3.1 Demographics

The birth date, gender, race, and ethnicity of each subject will be documented in the eCRF.

#### 9.3.2 Fitzpatrick Skin Types

Fitzpatrick skin types will be classified as follows:

- Type I: Pale white skin, always burns, and never tans.
- Type II: White skin, usually burns easily, tans minimally.
- Type III: Light brown skin, burns moderately, tans uniformly.
- Type IV: Moderate brown skin, burns minimally, always tans well.
- Type V: Dark brown, rarely burns, tans very easily.
- Type VI: Deeply pigmented dark brown to black skin, never burns deeply.

#### 9.3.3 Medical History

Medical history, including any diseases, all past surgeries including skin procedures, and psychiatric illnesses will be documented in the CRF of enrolled subjects.

Each subject will be questioned regarding any planned elective procedures that may occur during or following completion of the study, and these must be documented in the subject's medical record and the medical history section of the CRF.

## 9.4 Safety Measures

### 9.4.1 Adverse Events

The investigator will determine during the course of all study periods whether any AEs have occurred. Sections 15 and 16, respectively, contain additional information with regard to AEs and SAEs.

### 9.4.2 Vital Signs, Weight, Height, and BMI

Throughout the study, vital signs (resting blood pressure, heart rate, temperature, and respiratory rate) will be obtained with the subject sitting or lying, after the subject has rested for at least 2 minutes.

Heart rates are best obtained electronically, if available. If heart rate data are obtained electronically, the results may not be obtained from an ECG scheduled at the same time. If these data are obtained manually, a minimum observation period of 30 sec is required.

Respiratory rate will be determined following a minimum observation of 30 sec.

The subject's height and weight will be documented in the CRF during the Screening visit.

BMI calculations will be performed as per the BMI calculator on the National Heart, Lung, and Blood Institute web site:

[http://www.nhlbi.nih.gov/health/educational/lose\\_wt/BMI/bmicalc.htm](http://www.nhlbi.nih.gov/health/educational/lose_wt/BMI/bmicalc.htm). This site offers the option to enter either standard or metric data.

### 9.4.3 Physical Examination

The physical examinations performed during the trial will include skin, external eyes, oral cavity, nodes, lungs, heart, abdomen, extremities, and gross motor neurologic examination.

All abnormal acute and chronic findings must be recorded whether they are new or were recorded previously in the CRF. For example, a surgical scar should be recorded on every scheduled physical examination.

## 10. CLINICAL LABORATORY TESTS

Blood and urine sampling will occur as listed in Section 12.4 and the Table of Study Assessments (Section 7.2). All blood samples will be drawn, prepared, maintained, and shipped as per the study Clinical/PK Laboratory Manual. Blood sampling for all clinical laboratory tests should be performed following the fasting period prescribed in the manual.

The following tests will be performed at part of the Clinical Laboratory Tests:

a) **Hematology:** The hematology analysis will consist of the following tests:

- White Blood Cell Count
- White Blood Cell Differential in absolute numbers
- Hemoglobin
- Hematocrit
- Mean Corpuscular Volume
- Mean Corpuscular Hemoglobin Concentration
- Red Blood Cell Count
- Platelet Count

b) **Coagulation Profile:** The coagulation parameter analysis consists of the following tests:

- Prothrombin Time (PT) and/or International Normalized Ratio (INR)
- Activate Partial Thromboplastin (aPTT)

c) **Complete Clinical Chemistry:** The Complete Clinical Chemistry consists of the following tests:

 
• ALT
 
• AST
 
• Albumin
 
• Alkaline phosphatase
 
• Direct bilirubin
 
• Total bilirubin
 
• Blood urea nitrogen or urea
 
• Calcium
 
• Total cholesterol
 
• Chloride
 
• Creatinine
 
	
 
• Glucose
 
• Lactate dehydrogenase
 
• Inorganic phosphorus
 
• Potassium
 
• Total protein
 
• Sodium
 
• Triglycerides
 
• Uric acid
 
• Total CPK
 
• Glomerular filtration rate*
 

---	--

\*Estimated glomerular filtration rate will be calculated using the SOPs of CRL, the central clinical laboratory.

d) **Urinalysis:** The urinalysis consists of the following tests:

- Glucose
- Protein
- pH
- Ketones
- Erythrocytes
- Leucocytes
- Nitrites

**Note:** Urine with abnormal protein, erythrocyte, leucocyte, or nitrite results will undergo a reflex automated examination.

#### 10.1.1 Pregnancy Testing

The pregnancy testing will be performed on urine samples to be processed, assayed, and reported by site personnel as per the study Clinical/PK Laboratory Manual. The urine test must have a minimum sensitivity of 25 mIU for  $\beta$ -hCG per mL.

All women enrolled in the trial must have a negative urine pregnancy test at Screening and Day 1 Pre-Dose.

#### 10.1.2 Toxicology and Drug Screen (PK Study Sub-Cohort only)

The toxicology, drug, and alcohol testing will be performed on urine samples to be processed, assayed, and reported by site personnel as per the study Clinical/PK Laboratory Manual.

#### 10.1.3 Electrocardiogram

A standard, surface 12-lead ECG will be obtained as per the ERT manual at the time points listed in the Schedule of Assessments (Section 7.2).

ECGs will be interpreted by a Board-Certified cardiologist at ERT (Philadelphia, PA, USA). The QT interval results will be adjusted for rate using the Bazett (QTcB) and Fridericia (QTcF) corrections.

Cardiac dysrhythmias will be documented by occurrence (date and time), severity, type, and duration. Isolated premature ventricular contractions and supraventricular extra-systolic waveforms will not be considered clinically significant.

Two printouts (original copies) of each electrocardiogram will be stored in the subjects' medical records. ECGs will be assessed, signed, and dated by the Investigator (or designee).

All ECGs will be electronically transmitted to the central ECG laboratory for interpretation.

#### **10.1.4 Holter Monitoring (PK Study Sub-Cohort only)**

Subjects in the PK Study Sub-Cohort will undergo approximately 24-hours of continuous multi-lead cardiac telemetric monitoring from Day 28 (approximately 12 hours after the Day 27 dosing) through Day 29. Subjects will remove the monitors on Day 29, approximately 24 hours after they are attached, and return the Holter recorder at the Day 35 Visit.

ERT's instruction manual describes proper use and placement of these monitors. Site personnel will be trained regarding proper placement of the electrodes and recorders.

The purpose of the 24-hour cardiac Holter monitor recording is to allow ECGs to be extracted based upon the plasma PK findings.

#### **10.1.5 Local Skin Reaction Score**

The Investigator (or designee) will use the Local Skin Reaction (LSR) Score (see Section 22.1) to numerically assess the overall degree of erythema, edema, weeping / exudate, vesicles, erosions / ulcerations, scaling / dryness, scabbing / crusting, itching, or pain) in the Treatment Field on a 5-point scale, from 0 (none) to 4 (severe). This assessment will be performed on Day 1 Pre-Dose (baseline) and repeated at each subsequent visit. The individual scores for each potential finding will be recorded in the respective cells by the assessor.

In this trial LSRs will be collected independently of AEs. Details regarding reporting are included in Section 15.1.

#### **10.1.6 Once-Weekly Subject Contact**

Site personnel will contact each subject once-weekly during the Treatment Period. The goals of this contact are: (a) to review the Dosing Instruction Packet and Dosing Diary with each subject; (b) to answer any questions raised by the study participants; (c) to remind subjects of their upcoming site visit and any related activities; and (d) to remind subjects to bring their study drug to each site visit.

### **10.2 Pharmacokinetic Measures (PK Study Sub-Cohort only)**

A maximum of eighteen subjects will participate in the PK Study Sub-Cohort. Blood samples for measurement of plasma VDA-1102 and its primary metabolite jasmonic acid (JA) will be taken at Day 1 Pre-dose. Post-dose blood sampling will occur at the Days 7, Day 14, and Day 28 Visits at approximately 12 hours after the Day 6, Day 13, and Day 27 evening doses, respectively. On Day 28, the sample should be drawn as close to 12 hours after the previous evening's dose as possible, and additional samples should be drawn at approximately 15, 18, and 21 hours ( $\pm$ 30 mins) after the Day 27 evening dose. A final sample will be collected on Day 35. The exact time of each blood sampling will be recorded in the EDC.

VDA-1102 topical ointment  
CONFIDENTIAL

Further details regarding the PK blood sampling as well as PK sample handling, processing, storage, and shipping are included in the study Clinical/PK Laboratory Manual.

Non-compartmental PK parameters (e.g., AUC, Cmax, Tmax, t1/2) will be calculated, if possible.

## 11. PROCEDURES FOR EFFICACY EVALUATIONS

### 11.1 AK Lesions

#### 11.1.1 AK Lesion Grading

This trial will use the AK lesion clinical grading established by Olsen *et al* and as recommended by the International League of Dermatologic Societies and the European Dermatology Forum:

Grade 1 – mild (slightly palpable AK that are felt better than seen)

Grade 2 – moderate (moderately thick AK that are easily seen and felt)

Grade 3 - severe (very thick and/or obvious AK). Treatment Fields selected for this trial must not contain any Grade 3 AK lesions (see Section 11.1.2, below).

#### 11.1.2 AK Lesion Eligibility

In order to be eligible for this trial, the AK lesions must meet each of the following criteria:

- a. Grade 1 or Grade 2 AK lesions (Section 11.1.1);
- b. located on the subject's forehead, cheeks, or scalp but not on the lips, submandibular area, or neck;
- c. discrete (i.e., no borders are clearly touching one another);
- d. a maximum diameter 10 mm (inclusive) in any direction;
- e. non-hypertrophic and non-hyperkeratotic (i.e., no thick scale, horn, or > 1 mm raised above background skin); and
- f. not atrophic, acantholytic, pigmented, or Bowenoid.

#### 11.1.3 Treatment Field Selection

Any 25 cm^2 contiguous area on the face or scalp of the subject that contains 4-8 AK lesions that meet the requirements stated in AK Lesion Eligibility criteria (section 11.1.2) may be selected as the study Treatment Field. The Treatment Field will be selected at Screening and confirmed on Day 1 Pre-Dose. If the Treatment Field selected at Screening is no longer eligible at Day 1 Pre-Dose, a new Treatment Field may be selected on Day 1 Pre-Dose.

It is recommended that the Treatment Field be a square or rectangle and that is visible to the subject when looking in the mirror. Treatment Fields not visible to the subject when looking in the mirror are best managed by having a dosing partner help with the dosing. Dosing partners must accompany the subject on Day 1 so as to undergo training and testing like all the subjects who self-dose.

The Treatment Field or its outer border must **not** be:

- a) Within 2.5 cm (~1 inch) of either labial commissure of the mouth, lip vermillion border, palpebral fissure or a suspected or proven malignancy;
- b) Close to another active dermatologic process that could spread to the Treatment Field and interfere with the proper assessment of the Treatment Field and/or its included AK lesions; or
- c) So close to the eyebrows, beard, or other area with hair as to interfere with proper application of the study drug or assessment of the Treatment Field.

**NOTE: Ideally other AKs should NOT be adjacent to the border of the Treatment Field which could confound the AK lesion counting or identification of the Treatment Field at subsequent study visits.**

#### 11.1.4 Study Tools

The following 3 study tools will be used for Treatment Field selection, AK Lesion counts, Study Drug measurement, and Study Drug Application. The preliminary tools will be supplied by the Sponsor; Investigators (or designee) will prepare the final tools for use by the sites and the subject.

Examples of the 3 study tools appear in Section 22.2 (Treatment Field Map), Section 22.4 (Treatment Field Template), and Section 22.6 (Subject Dosing Card).

1. **Treatment Field Map** - This flexible, 8.5 x 11 inch plastic transparency with 1 cm x 1 cm grid printed on the surface will be used by the Investigator (or designee) to: (a) define a Treatment Field at Screening and Day 1 Pre-Dose Visits; (b) count AK lesions in the Treatment Field; and (c) to create the Treatment Field Template. Instructions regarding use of this tool appear in the Treatment Field Map Instructions (Section 22.3).
2. **Treatment Field Template** – The tool consists of a clear, thin, flexible, 8.5 x 11 inch plastic transparency sheet supplied by the Sponsor marked by the Investigator (or designee) with landmarks (e.g. eyebrows, ear helix, and/or nevi) to guide the subject to the proper placement of the sheet. The template also includes a cut-out hole that will act as a stencil, guiding the Subject (or dosing partner) to the precise Treatment Field for application of the study drug. This template (stencil) will be used by the:
  - a. Investigator (or designee) (a) to train the subject in proper identification of their unique Treatment Field; and (b) to train the subject in precise study drug application to their unique Treatment Field.

b. Subject (or dosing partner): (a) to identify their unique Treatment Field and (b) to apply the study drug precisely to their Treatment Field. Instructions regarding use of this tool appear in the Treatment Field Template Instructions (Section 22.5).

3. **Dosing Card** – a clear, thin, flexible plastic transparency with a rectangle printed on the back side. A strip of ointment expressed from the study drug tube that fits the clear portion of the rectangle is the correct approximate dose of study drug to be applied to the Treatment Field. A new previously unused Dosing Card will be used each evening by the subject to measure their proper study drug dose, and will be discarded after use. A sample of the Dosing Card is included in Section 22.6. Instructions regarding use of the Dosing Card are included in the Subject Instruction Packet.

### 11.1.5 AK Lesion Count

At the Screening and Day -1 Pre-Dose Visits, the selected Treatment Field must include at least four (4) and no more than eight (8) visible and discrete non-hyperkeratotic, non-hypertrophic AK lesions.

All AK lesions in the selected contiguous 25 cm^2 Treatment Field will be identified, counted, graded, and recorded at each visit.

If the subject has a LSR that prevents the investigator or designee from performing the AK count at a visit, the investigator or designee should document in the source document and CRF that the AK count was unable to be obtained due to a LSR.

### 11.1.6 Photography

Photography will be performed at designated study visit(s) at selected sites participating in this study as specified per protocol. The selected study sites will be provided with suggested guidelines to assist them in taking standardized photographs. However, it should be noted that all study sites, at the discretion of the investigator, may elect to photograph the subject under various magnification and lighting conditions to document the effects of treatment, adverse events or other findings during the trial. All photographs taken as part of this study are for informational purposes only and are not to assist in grading or for any other assessment.

Note: Subjects may decline to have photographs taken during the conduct of the study. If a subject initially consents to photographs, then declines further photography, the Sponsor may use the photographs taken under consent for the purposes noted.

## 12. CONDUCT OF THE STUDY

### 12.1 Study Blinding and Randomization

#### 12.1.1 Randomization

Assignment of study drug will be performed using a web-based Interactive Responsive Technology (IRT)-based randomization system. On Day 1 Pre-Dose, after confirming the subject's eligibility, the Investigator (or his designee) may approve the subject's blinded randomization.

The web-based IRT will randomize subjects in a fashion that will maintain a balance among the 3 treatment groups (5% and 10% VDA-1102, and placebo) across all subjects enrolled (not per site) and within the PK Study Sub-Cohort.

Subjects who withdraw or are terminated after 1 study dose has been applied will not be replaced in the trial.

Should a subject lose or destroy a tube, the IRT is capable of assigning additional study drug to each subject with the appropriate treatment assignment.

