### 7.4 PK Study Sub-Cohort

Of the approximate 84 subjects to be enrolled in this trial, a maximum of 18 subjects (who meet more stringent enrollment criteria than the other subjects enrolled) at select sites, will undergo blood sampling for PK analysis on Day 1 Pre-Dose as well as on Days 7, 14, 28, and 35 (Table 6). In addition, these subjects will undergo 24-hour cardiac Holter monitoring on Day 28 so that ECGs may be extracted based upon the other safety findings and the plasma PK data.

Subjects included in this sub-cohort may also be included in the Nested Phase 1b Safety Sub-Cohort if they are one of the first 15 subjects to be enrolled into the study.

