***Additional Exclusion Criteria for Subjects in the PK Study Sub-Cohort:***

17. Subject has a Body Mass Index (BMI) of  $\leq 18$  and  $\geq 35$ ;
18. Subject within 4 weeks of Screening had major blood loss or donated blood or a blood component;

19. Subject has any clinically significant medical abnormality or chronic disease that may interfere with the absorption, metabolism, or excretion of the investigational product. This includes such conditions as hepatic, renal, cardiac, or pulmonary disease or an estimated glomerular filtration rate <60 milliliters per minute;
20. Subject (self-reported) abused drugs or alcohol within 3 years of screening or used tobacco, smoking cessation products, or products containing nicotine within three months of Screening;
21. Subject has positive toxicology or drug, at Screening other than a benzodiazepine for sleep that the subject is willing to avoid during the trial and is negative upon re-test during Screening;
22. Subject is unable or unwilling avoid alcoholic beverages, smoking, nicotine products, and any medications unapproved by the Investigator from Screening through Day 35; or
23. Subject was exposed to any paint solvents or pesticides within 4 weeks of Screening.

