**✓ Day 1 Pre-Dose Visit**

Subjects who have completed all screening procedures and continue to meet the study enrollment criteria will return to the investigative site on Day 1 Pre-Dose. During this visit, the following procedures will be performed:

- Vital signs: oral temperature, peripheral blood pressure, heart rate, and respiratory rate will be recorded
- Adverse event(s): volunteered, elicited, and observed AEs will be recorded

- Concomitant medications documented
- Study Drug Measurement and Application review (see Section 13.6.3) should be one of the first procedures performed upon arrival at the site. The Treatment Field Map and Template will be prepared as per the Investigator instruction sheet.
- Subject will be trained to measure (using placebo ointment on the Dosing Card) and to accurately apply the study drug, without actually applying placebo ointment to their Treatment Field
- Physical examination
- Fitzpatrick skin typing (Section 9.3.2)
- Local Skin Reaction Score (baseline)
- AK Lesions in the Treatment Field: baseline count (11.1.5) and grading (11.1.1)
- Urine pregnancy test will be performed in all females and results recorded.
- 12-lead ECG tracing will be recorded as per the ERT manual. An original (duplicate) copy of the ECG is required for trial documentation. This ECG will also be transmitted to the central ECG laboratory
- Study Drug Application: Training and Testing (see Section 13.6.3) should be repeated after all the above activities have been completed. Subject will be trained to measure (using placebo ointment on the Dosing Card) and to accurately apply the study drug, without actually applying placebo ointment to their Treatment Field.
- Safety data from Screening, all available data from the Day 1 Pre-Dose Visit, as well as the Enrollment Criteria will be reviewed and approved by the Investigator (or designee)

Subjects who meet the study enrollment criteria will undergo the following procedures:

- Randomization of subjects
- Clinical laboratory tests: Fasting status will be recorded.
- Photographs of Treatment Field at designated sites
- Study drug weighed and recorded

Subjects enrolled in the **PK Study Sub-Cohort** will undergo the following additional procedure:

- ❖ Notify IWRS that the subject was enrolled in the PK Study Sub-Cohort to enable proper randomization and treatment assignment
- ❖ Blood sampling for (baseline) PK

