#### 5.5.4 Pharmacokinetic Population

5.5.4.1 The subjects (maximum of 18) enrolled in the PK Study Sub-Cohort at approximately 3 sites will constitute the PK population.

MediStat Statistics in Medicine	DOCUMENT NUMBER: 029-BST-PLN-001	PAGE: 28 of 45
TITLE: Statistical Analysis Plan for study:  A Phase 2 Randomized, Double-Blind, Placebo-Controlled, Parallel-Cohort Study to Evaluate the Efficacy, Safety, Tolerability, and Pharmacokinetics of Once-Daily Application of Topical VDA-1102 Ointment for 28 Days in Subjects with Actinic Keratosis	EFFECTIVE DATE : 22/MAY/2017 REVISION NUMBER : 2.0	

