## 5.6.5 Efficacy Primary Analysis

- 5.6.5.1 The efficacy analysis will be performed with the ITT, mITT and PP populations (see Tables 14.2-1 - 14.2-9). The primary efficacy endpoint is the decrease from baseline in number of AK lesions. The within-group decrease in number of AK lesions from baseline to each visit will be analyzed using paired t-test or signed rank test for two means (paired observations, as is appropriate).
- 5.6.5.2 Comparative analysis of the decrease at Day 56 (mentioned above) will be applied between each of the active groups versus the placebo group using the two-sample t-test, the non-parametric Wilcoxon-Mann-Whitney rank sum test for independent samples, or the Median test (as appropriate) and using the Analysis of Covariance (ANCOVA), after optionally ranking transformation of the variable, with adjustment for sites and for other covariates suspected as affecting the outcome and which will be found different between the treatment groups.
- 5.6.5.3 Figures depicting the number of lesions by visit and by treatment group and depicting the reduction in number of lesions from Baseline to Day 56 will be generated
- 5.6.5.4 Binary variable will be defined based on the decrease in number of AK lesions at Day 56 according to a relevant cutoff (first quartile, median, third quartile or other cutoff computed by ROC curve sensitivity analysis). Comparative analysis of this variable will be applied between each of the active groups versus the placebo group using Chi-square test or Fisher's Exact test and using logistic regression with adjustment for site and for other covariates suspected as affecting the outcome and which will be found different between the treatment groups.

	DOCUMENT NUMBER: 029-BST-PLN-001	PAGE: 31 of 45
TITLE: Statistical Analysis Plan for study:  A Phase 2 Randomized, Double-Blind, Placebo-Controlled, Parallel-Cohort Study to Evaluate the Efficacy, Safety, Tolerability, and Pharmacokinetics of Once-Daily Application of Topical VDA-1102 Ointment for 28 Days in Subjects with Actinic Keratosis	EFFECTIVE DATE : 22/MAY/2017 REVISION NUMBER : 2.0	

5.6.5.5 If the two active VDA-1102 groups trend similarly then these two groups may be pooled and compared to the placebo group in order to achieve higher statistical power.

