5.6.5.6 The overall effect and trend of differences in the decrease over time between the groups will be analyzed using a mixed-effect model for repeated measures. The model will include decrease from baseline at any time, the fixed effect time, and the interaction of treatment and time. Contrast will be calculated for each time point (Days 7, 14, 28 and 56) versus baseline and the overall effect. The model will be adjusted for site and for other covariates suspected as affecting the outcome and which will be found different between the treatment groups.

5.6.5.7 For the ANCOVA analysis, logistic regression and mixed-effect model for repeated measures detailed above, if necessary, grouping of sites will be done based on similarities and differences observed between sites by post-hoc contrasts of ANOVA.

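### Randomisation is balanced within the PK Study Sub-Cohort, but the SAP's efficacy models omit that factor and their covariate rule is very unlikely to bring it in

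*Protocol*

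**What the plan says.** **Allocation.** Protocol 12.1.1, repeated in SAP 5.2.5.2, balances the arms "across all subjects enrolled (not per site) and within the PK Study Sub-Cohort". The Day 1 Pre-Dose procedures (Protocol 12.4.1) tell staff to "Notify IWRS that the subject was enrolled in the PK Study Sub-Cohort to enable proper randomization and treatment assignment", so PK status enters the assignment. SAP 5.2.5.2 refers to a separate randomisation plan for details.

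**Who the PK subjects are.** Protocol 7.4 describes "a maximum of 18 subjects (who meet more stringent enrollment criteria than the other subjects enrolled) at select sites". Exclusions 17 to 23 (Protocol 8.2) apply only to them and cover BMI, blood loss, interfering chronic disease or reduced renal function, substance and nicotine use, toxicology, avoidance of alcohol and unapproved medication, and solvent exposure. SAP 5.5.4 places them at about 3 sites.

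**Efficacy models.** SAP 5.6.5.2 specifies the two-sample t-test, Wilcoxon or Median test, and an ANCOVA "with adjustment for sites and for other covariates suspected as affecting the outcome and which will be found different between the treatment groups". The logistic models (5.6.5.4, 5.6.6.4) and the mixed model (5.6.5.6) use the same rule. The protocol's models (17.2.1, 17.2.4) use the baseline count plus the same kind of conditional covariate. PK status is named in none of them.

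**The concern.** A factor used to balance the allocation normally belongs in the model whether or not the arms look balanced on it. Balancing removes the factor's contribution to the sampling variance of the treatment difference. If the model leaves the factor out, its residual variance still contains that contribution, so the standard error is too large whenever the factor predicts outcome.

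The SAP's rule points the opposite way. It adjusts for site, which was expressly not balanced, and admits other covariates only when an imbalance is observed. Balancing makes such an imbalance improbable for PK status, so the rule tends to exclude the one subject characteristic that the allocation controls.

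At stake is some precision and power in the modelled Day 56 comparison, in a trial with 25 evaluable subjects per arm and a planned power of 80%.

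**Working it through.** **Inputs from the documents.** Effect size 0.83, two-sided alpha 0.045, 25 evaluable per arm, 80% power, 10% drop-out, 84 recruited (Protocol 17.1, SAP 5.3.2). At most 18 PK subjects (Protocol 7.4), hence 6 per arm if the sub-cohort is full and balanced.

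**Assumed, because the documents give no figure.** The PK versus non-PK difference in mean lesion change, the SD of the change, and the block size.

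**1. The plan's own figure.** Noncentrality = 0.83 × √(25/2) = 2.93 with 48 df and critical t = 2.058, which gives power of 80.7% (79.0% at 24 per arm). Recruitment: 25/0.9 = 27.8, so 28 per arm and 84 in all. Both reproduce.

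**2. Would the covariate rule select PK status?** Balance tests with 28 per arm:

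| PK subjects per arm | Three-arm chi-square p |
|---|---|
| 6 / 6 / 6 | 1.00 |
| 7 / 6 / 5 | 0.81 |
| 8 / 6 / 4 | 0.43 |

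For two arms sharing 12 PK subjects, a 9 to 3 split gives Fisher p = 0.10. It takes 10 to 2 to fall below 0.05 (p = 0.020). In simulated permuted blocks of 3, 6 or 9 with 10 to 18 PK subjects, the smallest three-arm p was 0.53. Without balancing on PK status, p < 0.05 would occur in about 3.8% of trials.

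**3. Effect of leaving it out.** In a two-arm comparison the PK share is 6/25 = 0.24, and 0.24 × 0.76 = 0.1824. With a PK/non-PK difference D:

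- share of variance = 0.1824 × D² / SD²
- overstatement of the standard error = 1/√(1 − share)
- approximate type I error = 2 × P(T₄₈ > 2.058/√(1 − share))

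For D = 1 lesion:

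| Total SD | Share | SE overstated by | Critical value in effect | Approx. type I error |
|---|---|---|---|---|
| 2.5 | 0.1824/6.25 = 2.9% | 1.5% | 2.089 | 0.042 |
| 1.5 | 0.1824/2.25 = 8.1% | 4.3% | 2.147 | 0.037 |

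Simulation with 25 per arm, 6 of them PK, alpha 0.045 and no site term:

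| Total SD | Type I error, PK omitted / included | Power, PK omitted / included |
|---|---|---|
| 2.5 | 0.041 / 0.044 | 81.3% / 82.0% |
| 1.5 | 0.035 / 0.043 | 81.7% / 84.0% |

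The included column should be 0.045 in theory, so the simulation error is about 0.001 to 0.002. Within that error the formula agrees.

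**4. Sensitivity to the assumed difference** (100,000 runs, difference in within-stratum SDs):

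| Difference | Type I error, omitted / included | Power, omitted / included |
|---|---|---|
| 0 | 0.045 / 0.045 | 80.7% / 80.7% |
| 0.25 | 0.044 / 0.045 | 80.6% / 80.9% |
| 0.5 | 0.040 / 0.045 | 81.3% / 82.5% |
| 0.75 | 0.035 / 0.045 | 81.8% / 84.4% |
| 1.0 | 0.029 / 0.045 | 82.3% / 86.7% |

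At larger differences the analysis without the term also rises above 80.7%, because the balanced design has already reduced the true variance. The gain is the difference within each row, not the distance from 80.7%.

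**The case against.** **Prognostic value is not shown.** Exclusions 17 to 23 serve pharmacokinetic purposes, and the lesion and Treatment Field criteria (Protocol 11.1.2, 11.1.3) are the same for everyone. A reader might infer from the stricter entry criteria that PK subjects respond differently to a topical ointment. The documents do not support that, nor do they exclude it. This stands, and it makes the size of the effect an assumption.

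**The assumed differences are not small.** With SD 1.5 to 2.5, the planned drug effect is 0.83 × SD = 1.25 to 2.08 lesions, so a 1-lesion PK difference is 48% to 80% of it. This also stands, and larger differences deserve little weight.

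**Site is already in the models.** PK subjects come from about 3 sites, so site may absorb part of any PK difference. The gain beyond site adjustment was not calculated. Site is still only a partial stand-in: those sites are not barred from enrolling non-PK subjects, and SAP 5.6.5.7 allows sites to be grouped after looking at differences between them.

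**The rule could still select PK status.** It is tempting to say that it never will. The documents do not support so firm a statement: the threshold is unstated, the randomisation plan was not available, 18 is a maximum, and uneven loss of PK subjects from an analysis set could create an imbalance.

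**Logistic models differ.** The one-degree-of-freedom cost was shown only for a continuous outcome. With about 25 per arm and site terms present, a PK term confined to about 3 sites could give sparse cells or separation, and adjustment need not shrink the standard error of the log-odds ratio. This stands and limits the fix.

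**Conclusion.** The omission is real: the allocation balances on PK status, no efficacy model includes it, and the covariate rule works against its selection. The consequence is small and conditional. If PK status is prognostic, the test without it is conservative: about 0.035 to 0.041 against a nominal 0.045, with about 1 to 2 power points to be gained, for an assumed 1-lesion difference, total SD 1.5 to 2.5, 6 PK subjects per arm and no site term. If PK status is not prognostic, nothing is lost by omitting it.

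A reader might infer that false-positive error is inflated or the treatment estimate biased. Neither follows, because the error runs in the conservative direction and the arms are balanced on the factor. A reader might also take the whole rise above 80.7% as the gain from adjustment; the omitted and included columns show that it is smaller. This is a free improvement to the SAP, not a defect that threatens the trial's conclusion.

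**What to change.** In SAP 5.6.5.2 and 5.6.5.6, pre-specify PK Study Sub-Cohort membership (yes/no), as recorded at randomisation, as a fixed term in the ANCOVA and in the mixed model, whatever the observed balance. State that the imbalance condition does not apply to this term.

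In the logistic models of 5.6.5.4 and 5.6.6.4, include the term only where cell counts allow stable estimation alongside the site terms, and set that criterion in advance.

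The cost is a few words in the SAP and, in the linear models, one degree of freedom (48 to 47 in the two-arm calculation, with no visible loss of power when PK status has no effect). The variable is already sent to the randomisation system. The unadjusted t-test, Wilcoxon and Median tests are not changed by this fix.
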